### A. Specific Aims

Aim 1: *To test the behavioral effects of tDCS during social rejection.* The first step will be to obtain behavioral effects of transcranial direct current stimulation (tDCS) during social rejection without functional magnetic resonance imaging (fMRI). Whereas previous studies used Cyberball (a computerized ball-tossing game that simulates social exclusion), we will use the Social Feedback Task. This task was created by [name] to be more ethologically-relevant, has been shown to sustain negative moods during rejection, and activates the right ventral lateral prefrontal cortex (rVLPFC) (preliminary fMRI data from 50 healthy controls in [name] previous study). Anodal tDCS will be applied over the right or left VLPFC to measure changes in mood during rejection and neutral conditions. Depending on results, alternate regions in separate subjects may also be stimulated: dorsolateral prefrontal cortex, insula, anterior cingulate cortex, pre-supplementary, and supplementary motor area [all regions may be right or left hemisphere]. All of these regions have been shown to be involved in emotion regulation. Questionnaires will be given before, during, and after the task to assess cognitive and emotional states.

Aim 2: *To identify neural pathways regulating negative moods during social rejection, using tDCS for activation and fMRI for assessment.* Using a cross-over, sham-controlled design similar to previous tDCS+fMRI studies, we will measure the effects of anodal tDCS over the right or left VLPFC on neural activity and negative mood during rejection and neutral conditions. Alternate regions in separate subjects may also be stimulated including the dorsolateral prefrontal cortex, insula, anterior cingulate cortex, pre-supplementary, and supplementary motor area [all regions may be right or left hemisphere]. All of these regions have been shown to be involved in emotion regulation.

### B. Background and Significance

Social acceptance into groups and intimate relationships are necessary for survival and emotional well-being. Actual or perceived threats to this need can produce strong negative moods and social withdrawal.

Neuroimaging studies by [name] and several others have identified brain regions activated during social rejection (i.e., when one is not wanted or liked). However the cause-and-effect of these activations is unclear: are they activated to enhance negative affect, or do they activate in order to decrease negative affect?

Recent studies have attempted to answer this by using tDCS, a safe and non-invasive form of neurostimulation that affects neuronal excitability. These studies provided tDCS over the rVLPFC, a region previously shown to be associated with *diminished* distress during rejection, and found that anodal tDCS reduced hurt feelings and aggression, whereas cathodal tDCS (producing the opposite current) increased hurt feelings during rejection. Importantly however, these studies did not examine the neural mechanisms associated with these changes. The **goal** of the present study is to activate and identify neural pathways regulating negative moods during rejection by combining tDCS and fMRI in a sample of healthy volunteers.

Whereas tDCS affects neuronal excitability, tDCS combined with fMRI has the potential to allow for causal inferences about neural activity and behavior. At the end of this project, we will have identified neural pathways regulating mood during social rejection. This will provide preliminary data for future projects that will combine tDCS and fMRI for investigating dysregulated responses to rejection in psychiatric populations such those with major depressive, social anxiety, and borderline personality disorders. Data from this study may also provide a rationale for testing tDCS as a safe, novel, inexpensive, non-pharmacological, and non-invasive treatment for these disorders.

## **D. Research Design and Methods**

### *1. Rationale/Overview*

We will first test the behavioral effects of tDCS during the Social Feedback Task without fMRI in a sample of up to 30 subjects. After establishing the behavioral effects of tDCS-only (Aim 1), we will test a separate group of up to 30 subjects using tDCS plus fMRI (Aim 2).

### *2. Research Site*

Consent, research interviews, assessments, and testing will take place at Stony Brook University in a closed office with only members of the research group present. The tDCS-only portion of this study (Aim 1) will be conducted at the Stony Brook Center for Understanding Biology using Imaging Technology (CUBIT) & the Stony Brook Mood+Anxiety Research+Treatment (SMART) Center, both located at the Stony Brook University Medical Center. The tDCS+fMRI portion of the study (Aim 2) will be conducted at the Social, Cognitive, and Affective Neuroscience (SCAN) Center located on West Campus. These sites include a comfortable waiting area, adequate space for researchers and coordinators, as well as computers, telephones, and additional supplies. Consent covering the procedures will be obtained at Stony Brook. In order to give subjects adequate time to read and consider the procedures, a copy of the informed consent form may be mailed by post or email to subjects before their first in-person meeting. All staff participating in this study will be fully informed about the protocol and their trial-related duties. All staff screening and evaluating subjects will be trained on administering scales, and all staff involved with imaging will be trained on the protocol used and their roles.

The Center for Understanding Biology using Imaging Technology (CUBIT) and the Stony Brook Mood+Anxiety Research+Treatment (SMART) Center, both located at Stony Brook University Medical Center, actively and regularly recruit research participants. These sites include adequate space for researchers and

coordinators, as well as computers, printers, telephones, and additional supplies. Based on previous recruitment, we estimate being able to recruit five subjects a month over a 12-month period.

### *3. Study Sample*

60 subjects (ages 18-25 years) in total will be included. We chose to study young adults since the exploration of intimate relationships is particularly important in this age group. Recruitment and screening will be conducted in up to 75 participants. Male and female representation will be about equal. No ethnic/racial/gender group is excluded.

### *4. Assessments*

Recruitment. We will recruit healthy men and women for Aim 1 (n = 30) and a separate group of healthy men and women for Aim 2 (n = 30) through flyers distributed throughout the SBU campus/greater Suffolk County area, the SBU psychiatry research volunteers website, the internet (e.g., Craigslist, Facebook, etc.) and the subject pool in the Psychology Department at Stony Brook University (IRB-approved Mass Testing, which uses the General Consent Form). All potential subjects will first come into contact with a research team member via phone, email, or in person.

Phone or Email Screen (5-10 minutes). If the subject is interested in participating in the study, s/he will be asked a series of initial screening questions (approximately 5 minutes) to determine initial eligibility. Verbal consent will be obtained prior to asking questions on the phone screen. The phone screen for initial eligibility will include: age 18-25, no current or previous diagnosis of psychiatric disorders, no current use of psychotropic drugs, no previous experience with tDCS, right-handedness, and not currently in a romantic relationship. Since being in a romantic relationship is anticipated to be a common exclusion factor, we will ask this question during the initial phone/email screen.

The purpose for including subjects who are not currently in a romantic relationship is to maximize the emotional saliency of romantic rejection. Our preliminary data suggests that responses to social feedback are dependent on relationship status. However, if a subject considers him/herself to not be in a romantic relationship but are also not “single” (e.g., separated spouses), they would be eligible provided that they can answer “no” to the question “are you currently in a romantic relationship?” We will inform potential volunteers that this study requires them to rate others with whom they would like to form a potential relationship, and so it is important that they are comfortable doing so, and not currently in a romantic relationship. As described below, the Social Feedback Task does not involve deception and subjects will be informed that the ratings given to them are not real – they are created and compiled by the experimenter. This task is identical to a current protocol approved at Stony Brook University (IRBNet ID: 698463) and has been published. After being given this information, the potential participant will define for her/himself whether or not s/he is in a romantic relationship, and decide if s/he would like to participate.

After qualifying for eligibility, the subject will be scheduled to come to Stony Brook for an in-person interview (Screening Visit). Verbal consent will be obtained for the screening procedures, which on Days 2 and 3 includes a urine toxicology screen for drugs of abuse and a urine pregnancy test for women. These urine tests will be performed at the Health Science Center exam room (T10) and the SCAN Center restroom/locker room.

Screening Visit. Subjects will be screened for the following inclusion and exclusion criteria:

Inclusion Criteria:

1. Healthy males or females between 18 and 25 years old
2. No diagnosis on Axis I by SCID or MINI. No current, or within the past 5 years.

3. Not currently in a romantic relationship
4. Ability to understand and follow instructions and oriented to name, time, and place.
5. No additional neurologic or psychiatric disorders
6. No current use of psychotropic drugs or during past 3 months (except marijuana and alcohol)
7. No current use of marijuana or during past 3 weeks
8. Not currently abusing alcohol
9. No history of alcohol or drug dependence within past 5 years
10. A negative urine pregnancy and toxicology screen. Verbal affirmation will be obtained (i.e., “not pregnant” and “not currently using psychotropic drugs or during the past 3 months”) during the Screening Visit (Day 1). Urine screen will be obtained on Days 2 and 3. If subject reports that there is a “possibility that she is pregnant” on Day 1 (Screening Visit) a urine pregnancy screen will be performed on that day.
11. (Women): If stopped or started oral contraceptives recently, at least 60 days on/off oral contraceptives.

#### Exclusion Criteria:

1. Left-handed or ambidextrous
2. Metallic dental implants
3. Metallic objects in the brain/skull
4. Medical device implants
5. Implanted electronic devices
6. History of seizures
7. History of strokes
8. Unexplained loss of consciousness
9. Frequent or severe headaches or neck pain
10. Clinically significant, uncontrolled liver, kidney, cardiac, or pulmonary disease
11. Terminal medical diagnosis consistent with survival < 1 year
12. Pregnancy; childbirth or miscarriage within 6 months, breastfeeding within 6 months of recruitment
13. Serious mental impairment. Mini mental state exam of < 23/30
14. Chronic skin disease
15. Previous experience with tDCS
16. Regular tobacco use or tobacco use within past month
17. If using hormonal birth control, taking progestin-only pills (e.g., Cerazette, Ovrette), or IUDs (Mirena, Skyla), since progestin-only birth controls are more likely to cause mood swings.

#### Addition Exclusion Criteria for participating in fMRI:

1. Metal anywhere in the body
2. Weight over 250 pounds, or girth size incompatible for scanner bore.

#### 5. Procedures

If the subject meets eligibility criteria during the screening visit, s/he will review the consent form with the study coordinator and provide written consent if willing to participate. The subject will then be scheduled for tDCS-only testing or tDCS+fMRI testing. The subject will be asked to complete online and/or paper questionnaires during the same visit (Day 1). Questionnaires (comprising of profile ratings and trait questionnaires) may also be completed at home. Urine pregnancy and toxicology screens are obtained on the day of testing. We may provide participants with a brief (up to 4 minutes) tDCS session to serve as an example for the set-up procedure and sensations to expect on the stimulation days (Day 2 and Day 3).

(For women): Preliminary data show that hormone fluctuations during the menstrual cycle may affect mood. Thus, we will ask women when their last menstruation occurred, if they are regular or irregular, and how many

days on average is their period. The date of their last menstruation will be asked during the screening visit, and on the days of the testing sessions (tDCS/fMRI). In addition, subjects are informed that they will be contacted 1 to 2 weeks after their next anticipated menstruation to determine the date of subsequent menses and assist with confirming menstrual phase during tDCS/fMRI. The scheduling of the tDCS/fMRI sessions may depend on phase in menstrual cycle.

Personal Profile Ratings: Prior to testing (in either tDCS-only or tDCS+fMRI), all subjects will complete an online profile (e.g., gender, age, birthdate, race/ethnicity, orientation, major/occupation, hobbies, personal qualities, years of education, etc.) and provide a digital photo of her/himself prior to rating online profiles of others. If subjects do not have a photo available or prefer, they may have a digital photo taken during the interview.

All subjects complete online ratings of personal profiles of the preferred sex from a collection of over 500 men and women with whom they would be most interested in forming a close personal relationship, as previously described. This procedure increases feedback saliency, since only profiles with the highest ratings are used.

Social Feedback Task: During the Social Feedback Task (presented on a personal computer) subjects are presented with their own picture along with a picture of a highly rated profile, along with feedback that they were liked (acceptance trial), not liked (rejection trial), or that others were undecided or had not yet rated them (neutral trial). Each run will consist of alternating condition blocks, with cross-hair fixation between blocks, similar to the fMRI study design from [name] previous projects. The total duration of the task is approximately 10 minutes. Questionnaires will be given before, during, and/or after the task to assess cognitive and emotional states. For questionnaires, answer choices may be presented on Likert scale (e.g., 5 discrete choices), or a visual analogue scale (e.g., a sliding scale), on paper or a computer. If time permits, subjects will perform an imagery training session (lasting about 2 minutes) in which they are asked to imagine that they are at their home computer. The purpose of this is provide a realistic scenario for them to imagine while they are performing the Social Feedback Task.

Balloon Analogue Risk Task: If time permits, subjects will also perform the Balloon Analogue Risk Task (BART). The BART is a computerized measure of risk taking behavior. Participants are presented with a cartoon balloon and offered the chance to earn points by pumping up the balloon by pressing a button. Each press causes the balloon to inflate and points to be added to a counter up until some threshold, at which point the balloon explodes and earnings are lost. Thus, the number of pumps is a measure of risk-taking.

Wheel of Fortune Task: If time permits, subjects will perform the Wheel of Fortune task (WoF). The WoF is a computerized measure of risk taking behavior. Participants are presented with a circle divided into two colors. The colors and sizes of the divisions represent different point values and probabilities. If the participant chooses correctly, they will win the points assigned to the chosen color. Otherwise, they don't get any points for the round. How frequently the participant chooses a low probability, high reward color is a measure of risk-taking.

Stop Signal Task: If time permits, subjects will perform the Stop Signal Task (SST). The SST is a computerized measure of response inhibition and attention. During the task, participants are instructed to quickly identify and respond to stimuli presented (e.g., the direction of an arrow). Occasionally, participants will receive a cue indicating that they are to withhold their response. Response times and correct/incorrect responses are collected.

Emotion Face Recognition Task: If time permits, subjects will perform a task requiring them to identify the emotion type or intensity depicted on pictures of faces. This task will allow the measurement of emotion recognition bias.

tDCS: The intervention, tDCS, is commercially available and consists of a small battery-driven device connected to electrodes. The scalp is inspected for any pre-existing irritation, cuts, or lesions to avoid stimulating over damaged skin. Subjects are seated comfortably (or lying in the scanner), and the locations of electrode placements are identified using landmarks on the head (e.g., using the EEG 10-20 system). Stimulation begins with a brief “ramping up” period (potentially resulting in a tingling sensation on the scalp) when the stimulation is gradually increased to the desired current (up to 2 mA), and “ramp down” period. By way of comparison, small hearing aids run on approximately 2.4 millamps. The sham condition may consist of stimulation through a different electrode placement (up to 30 minutes; up to 2 mA) or with a shorter duration (up to 2 minutes) than the active condition. This sham procedure has been shown to be indiscernible from active tDCS. In the active condition, the current will be maintained for the duration of the block (up to 30 minutes).

tDCS-only study: Testing will occur over two sessions (sham or active, counter-balanced order between subjects). The two sessions will be separated by at least 5 days in order to minimize potential carry-over effects. In each session, tDCS (or sham) will begin prior to the Social Feedback Task, and may be maintained for the duration of the task or cease before the Social Feedback Task begins.

tDCS+fMRI study: Testing will occur over two sessions (sham or active, counter-balanced order between subjects). The two sessions will be separated by at least 5 days in order to minimize potential carry-over effects. In each session, tDCS (or sham) will occur prior to or concurrent with fMRI scanning and the Social Feedback Task. Structural and resting state fMRI will also be acquired during this session.

Questionnaires (administered in person or over internet): Adult Rejection Sensitivity Questionnaire, Brief Fear of Negative Evaluation Scale, Brief Resilience Scale, Difficulties in Emotion Regulation Scale, Ego Resilience Scale, Emotion measures following social feedback, Emotion Regulation Questionnaire, Hurt Feelings, Interpersonal Sensitivity Measure, Mini Mental State Exam, Multidimensional Scale of Perceived Social Support, PANAS-X, Rosenberg Self-Esteem Scale, Ruminative Responses Scale, Sensitivity to Rejection Scale, Social Feedback/tDCS Follow-up, Social Resilience Scale, Sociability Survey, State Self-Esteem, Structured Clinical Interview or MINI International Neuropsychiatric Interview, tDCS Sensation Questionnaire, Teasing Questionnaire-Revised, Visual Analogue Scale, State Rumination Measure. For questionnaires, answer choices may be presented on Likert scale (e.g., 5 discrete choices), or a visual analogue scale (e.g., a sliding scale), on paper or a computer.

Additional surveys to be completed if time permits (administered in person or over internet): Appearance-based Rejection Sensitivity Scale (Short Form), Barratt Impulsiveness Scale, BIS/BAS, Buss-Perry Aggression Questionnaire, Delayed Discounting, Drinking Motives Questionnaire, Experiences in Close Relationships Inventory, International Personality Item Pool, Interpersonal Needs Questionnaire, Interpersonal Dependency Inventory, Interpersonal Reactivity Index, NIAAA Recommended Alcohol Questions, Personality Inventory for DSM-5, Retrospective Bullying Questionnaire, Shyness and Sociability, Single-Item Self-Esteem Questionnaire, Social Anhedonia Scale-Revised, Social Network Index, Social Reward Questionnaire, UCLA Loneliness Scale (trait and state), UPPS-P (Urgency, premeditation, perseverance, sensation seeking, and positive urgency), Dimensional Anhedonia Rating Scale, Anticipatory and Consummatory Interpersonal Pleasure Scale (ACIPS), Hook Up Motives Questionnaire, State Hook Up Approval Rating, Trait Hook Up Behavior Rating, Imagery question. For questionnaires, answer choices may be presented on Likert scale (e.g., 5 discrete choices), or a visual analogue scale (e.g., a sliding scale), on paper or a computer.

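### The optional example tDCS session, most naturally given on Day 1, is not tied to a urine pregnancy test, so a woman could receive study current on verbal affirmation alone

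*Combined protocol and SAP*

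**What the plan says.** Section D.5 (Procedures) opens with what happens once a subject is found eligible at the screening visit: written consent, then scheduling ("The subject will then be scheduled for tDCS-only testing or tDCS+fMRI testing"), then questionnaires ("The subject will be asked to complete online and/or paper questionnaires during the same visit (Day 1"). The same paragraph says that urine screens are done on the testing day. Its last sentence introduces the example session: "We may provide participants with a brief (up to 4 minutes) tDCS session to serve as an example". The stated purpose is to show the set-up and the "sensations to expect on the stimulation days (Day 2 and Day 3". No day is given for the session, and no urine test is attached to it.

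Pregnancy is dealt with in section D.4 (Assessments):

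- Exclusion item 12 reads "Pregnancy; childbirth or miscarriage within 6 months, breastfeeding within 6 months of recruitment".
- Inclusion item 10 requires a negative urine pregnancy and toxicology screen and staggers the check. Day 1 relies on verbal affirmation, and then "Urine screen will be obtained on Days 2 and 3". If a woman says on Day 1 that she might be pregnant, "a urine pregnancy screen will be performed on that day".
- The text before the criteria, on what screening involves, gives the same schedule: "which on Days 2 and 3 includes a urine toxicology screen for drugs of abuse and a urine pregnancy test for women".

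**The concern.** The plan makes a negative urine pregnancy test a condition of inclusion, so it does not treat a woman's own report as sufficient for the study as a whole. Yet it permits a short application of study current at a point where, on the most natural reading, her own report is all there is. The urine test that can occur on Day 1 is triggered by her saying that pregnancy is possible. It therefore misses the case that a urine test exists to catch, a pregnancy of which she is unaware.

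What is at stake is participant protection and consistency between the eligibility criteria and the order of procedures. The subjects are healthy volunteers aged 18 to 25 who, by section G, receive no personal benefit. Applying the plan's own safeguard before any current is therefore a reasonable minimum.

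**Working it through.** The plan states no figure on this point to reproduce. The check is a comparison of texts, followed by a short count.

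**Step 1. When is the example session given?** Section D.5 does not say. Two cues point to Day 1. The paragraph is otherwise mainly about the screening visit, which it labels Day 1. The session also prepares subjects for stimulation on Days 2 and 3, and a preview comes before the thing previewed. This is an inference, not a statement in the plan.

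**Step 2. Which pregnancy checks come before it on Day 1?**

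| Check | Where | Covers an unsuspected pregnancy before the example session? |
|---|---|---|
| Phone or email screen | D.4 | No; no pregnancy question is listed |
| Verbal affirmation, Day 1 | D.4, inclusion item 10 | No; depends on the woman knowing |
| Urine test on Day 1 if she reports a possibility | D.4, inclusion item 10 | No; triggered by self-report |
| Date of last menstruation, Day 1 | D.5 | Not designed to; asked because the cycle may affect mood |
| Routine urine test, Days 2 and 3 | D.4 | No; comes later |

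**Step 3. Does the testing-day sentence in D.5 close the gap?** Not clearly. D.5 has the subject scheduled for testing after the screening visit. Its descriptions of the tDCS-only and tDCS+fMRI studies define testing as two sessions, one sham and one active. D.4 twice fixes the urine screens to Days 2 and 3. On that usage the example session is not testing.

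**Step 4. How many women?** Section D.3 (Study Sample) gives 60 subjects, with the sexes about equally represented.

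- Included women: 60 × 0.5 = 30.
- Pregnancy tests already planned: 30 women × 2 days = 60.
- Extra tests if every included woman is given the session and is tested first: 30 × 1 = 30, that is 30/60 = 50% more.
- If the session is not used: 0.

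The 30 is a ceiling on included women who might receive current without a urine test. It is not a number of pregnancies; the documents give no basis for estimating that.

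**The case against.** The strongest reply is that the gap rests on a day the plan never states. The sentence on urine screens stands immediately before the one on the example session. One could read the session as given at a testing visit once the screen is done, in which case nothing is missing. That reading is possible, but it fits the preview purpose less well. Even then, the text does not say that the urine result must come before the example current. What stands is that Day 1 is inferred and that the session is optional.

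A second reply is that item 10 sets up a staged check, and a Day 1 session after verbal affirmation complies with the stage then due. That is right: no one following the plan would be breaching it. What remains is that the urine stage is still outstanding when current is applied.

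A third reply is that no harm is shown. This also stands. The session lasts 4 minutes at most, section G expects side effects to be mild and brief, and the documents report no harm from brief tDCS in pregnancy. Nor does the plan say why pregnancy is excluded. Its remarks on hormones and mood make confounding of the mood outcomes at least as visible a reason as fetal safety.

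A reader might infer more than this: that the plan definitely gives current to untested women, that a fetus would be put at known risk, or that the results are compromised. The documents support none of these. The first depends on an unstated day and an optional procedure, and the second has no evidence in the text. The third fails because urine screens are already due on Days 2 and 3. A reader might also count every screened woman as exposed, but D.5 puts eligibility and written consent first, so included women are the relevant group.

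**Conclusion.** The point holds as a minor participant-protection gap. As written, the plan allows up to 4 minutes of study current to reach a woman who does not suspect a pregnancy, on verbal affirmation alone, before the urine part of item 10 is met. At most about 30 included women could be affected, and none if the session is not used. This rests on two assumptions: that the session takes place on Day 1, and that about half of the 60 subjects are women. The absolute risk is probably low. Sample size, power, error rates and the outcome data are not affected.

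**What to change.** In section D.5, state that the example session takes place on Day 1 after written consent, and that any woman given it must first have a negative urine pregnancy test that day. In inclusion item 10 of section D.4, extend the Day 1 urine test, now reserved for women who report a possible pregnancy, to every woman who will receive the session.

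The cost is one or two sentences of amendment and about 30 extra pregnancy kits at most, on top of about 60 already planned. A woman already tested on Day 1 because she reported a possible pregnancy needs no second kit. If the session is not used, no kits are needed.

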## **E. Data Analysis**

tDCS-only: Measures of cognitive and emotional states will be compared within subjects for sham vs. active tDCS. These changes may also be correlated with trait measures.

**tDCS+fMRI:** Our fMRI data will be analyzed with Statistical Parametric Mapping v.8 (SPM8). We will first conduct a hypothesis-driven region of interest (ROI) analysis (Bonferroni-corrected alphas for multiple VOIs) to examine brain areas previously shown to be activated during rejection including the rVLPFC, anterior insula, and dorsal anterior cingulate. We will compare rejection-neutral contrasts between runs and sessions, in a within-subjects analysis. We will also conduct a whole-brain analysis in a voxel-by-voxel brain-wide search. Statistical parametric maps are obtained using whole-brain image subtraction routines with the images warped to MNI standardized space. Differences between tDCS and sham are then mapped into stereotactic space using t-maps of statistical significance using a general linear model. RS as a covariate will also be tested in both the VOI and whole-brain analyses.

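### Does the Aim 1 active-versus-sham mood comparison need a menstrual-phase term, given that phase is recorded at both sessions?

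*Combined protocol and SAP*

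**What the plan says.** Under D.5 Procedures, the paragraph for women gives the motive, "Preliminary data show that hormone fluctuations during the menstrual cycle may affect mood". Dates of last menstruation are taken at screening and on each testing day, and a later contact serves to "determine the date of subsequent menses and assist with confirming menstrual phase during tDCS/fMRI". On design-stage control it says only "The scheduling of the tDCS/fMRI sessions may depend on phase in menstrual cycle".

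The tDCS-only study is a two-period crossover: "Testing will occur over two sessions (sham or active, counter-balanced order between subjects". On spacing, "The two sessions will be separated by at least 5 days", with no upper limit. The inclusion criteria in D.4 require women who recently started or stopped oral contraceptives to have been "at least 60 days on/off oral contraceptives", and the exclusion criteria remove users of progestin-only methods. D.3 adds "Male and female representation will be about equal".

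For Aim 1, Section E states "Measures of cognitive and emotional states will be compared within subjects for sham vs. active tDCS" and allows correlation of the changes with trait measures. The only covariate it names is RS, for the imaging analyses. Section A describes the Aim 1 outcome as change in mood under both the rejection and the neutral condition.

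**The concern.** The plan names a cause of mood variation, collects what is needed to measure it, and gives it no place in the analysis of a mood outcome. Pairing removes only what is constant within a woman. Her two sessions can fall in different phases, because phase-based scheduling is optional and the gap has a minimum only. For such a woman, the phase difference goes straight into her active-minus-sham difference.

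Precision would be at stake. Aim 1 has up to 30 subjects, about half of them women, so a modest inflation of the standard error could matter. There is also a question of discretion: with phase data in hand and no stated rule, an analyst could decide whether to adjust after seeing the result.

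**Working it through.** The plan states no power, alpha, effect size or SD for Aim 1, so there is no figure to reproduce. The check asks how much a phase term would gain or cost.

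**Inputs from the plan.** n = 30 (D.1), about 15 women (D.3, if the overall split applies to Aim 1), gap of at least 5 days, counterbalanced order (D.5).

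**Assumptions.** A 28-day cycle with two 14-day phases and a random start day; 15 or 10 naturally cycling women, since oral contraceptive users can be eligible; phase effect φ of 0.25, 0.5 or 1.0 in SDs of the paired difference.

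**Model.** D = δ + φ·x + e, with SD(e) = 1 and x = phase at active minus phase at sham (+1, 0 or −1; 0 for men and non-cycling women).

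**1. Bias.** Let c be the cycling share of the sample, P the probability that a cycling woman's sessions differ in phase, and π the share of those women whose active session falls in the adverse phase. Bias = c·P·φ·(2π − 1). When order is independent of phase, π = 0.5 and the bias is 0. In simulation (15/15 counterbalanced order), the mean error was at most 0.002 SD and the type I error of the unadjusted test 4.5% to 5.0%.

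**2. Probability of different phases.** P = 2g/28 for a gap of g days up to 14. At 5 days P = 10/28 = 0.357; at 14 days P = 1.

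**3. Standard error without a phase term.** Ratio to a comparison free of phase noise = √(1 + c·P·φ²).

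| Cycling | P | φ = 0.25 | φ = 0.5 | φ = 1.0 |
|---|---|---|---|---|
| 15 of 30 | 0.357 | 1.006 | 1.022 | 1.086 |
| 15 of 30 | 1 | 1.016 | 1.061 | 1.225 |
| 10 of 30 | 0.357 | 1.004 | 1.015 | 1.058 |
| 10 of 30 | 1 | 1.010 | 1.041 | 1.155 |

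Chance imbalance in phase is already inside these ratios. For c = 0.5, P = 1, φ = 0.5, its SD is 0.5 × √(0.5/30) = 0.065, against a base standard error of 1/√30 = 0.183. Combined, √(0.183² + 0.065²) = 0.194, and 0.194/0.183 is about 1.06, as in the table.

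**4. Net of the cost of adjusting.** A fitted phase term uses a degree of freedom and a slope estimate. Mean 95% CI half-widths by simulation (15 cycling, phase known without error):

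| P | φ | Unadjusted | Adjusted | Unadjusted relative to adjusted |
|---|---|---|---|---|
| 0.357 | 0 | 0.3701 | 0.3771 | 1.9% narrower |
| 0.357 | 0.25 | 0.3725 | 0.3775 | 1.3% narrower |
| 0.357 | 0.5 | 0.3779 | 0.3768 | 0.3% wider |
| 0.357 | 1.0 | 0.4017 | 0.3772 | 6.5% wider |
| 1 | 0.25 | 0.3762 | 0.3775 | 0.3% narrower |
| 1 | 0.5 | 0.3933 | 0.3779 | 4.1% wider |
| 1 | 1.0 | 0.4541 | 0.3773 | 20% wider |

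**5. Break-even.** (0.3771/0.3701)² − 1 = 0.0382 = c·P·φ². With 15 cycling, φ = √(0.0382/(0.5 × 0.357)) = 0.46 at a 5-day gap and √(0.0382/0.5) = 0.28 if all are discordant. With 10 cycling, the values are 0.57 and 0.34. Below these, adjustment loses precision.

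**6. Phase measured with error.** Phase would come from self-reported dates. With an assumed 20% of sessions misclassified (15 cycling), the unadjusted interval relative to the adjusted one is 1.2% narrower (φ = 0.5) or 0.6% wider (φ = 1.0) at a 5-day gap, and 1.1% or 8.1% wider if all are discordant. The best case of 20% falls to 8.1%, and the gain at a 5-day gap almost vanishes.

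**The case for a change.** The best argument for a phase term is that its costs and gains are unequal: at worst about 1.9% of interval width, against up to 20%. In power terms, take the standardised effect of 0.529 that 30 subjects detect with 80% power (two-sided 0.05 assumed). Without the term, power is 78.3% for an effect of 0.5 SD at a 5-day gap, 75.2% if all women are discordant, and 62.9% for an effect of 1 SD with all discordant. The term needs one sentence, and a fixed rule would remove analyst discretion. Design does not fully settle the matter either: scheduling by phase is optional, the contraceptive criteria leave naturally cycling women untouched, and order is called counterbalanced without being called randomised or balanced among women. If order were tied to phase, with π = 0.75 and φ = 0.5, the bias would be 0.5 × 0.357 × 0.5 × 0.5 = 0.045 SD at a 5-day gap, or 0.125 SD with all discordant.

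Much of this stands as description. Section E is silent on phase, and the dates have no stated analytic use. But the upper end of the gain needs a 1 SD phase effect, 15 naturally cycling women and a change of phase in every one of them. The plan says only that mood may be affected. Nothing in it links order to phase, and any phase-based scheduling that is done could reduce discordance, for which the model gives no credit.

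Two further points weaken the case. Section A puts mood in both the rejection and neutral conditions within Aim 1. Section E can be read as comparing session scores, but if the analysis uses rejection minus neutral or change within a session, a general-mood phase effect largely cancels, as it does in the Aim 2 contrast. And phase would not always be derivable: if two menses fall between sessions, the first may never be recorded, and in a long cycle the follow-up contact may come before the next menses.

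**Conclusion.** The concern does not call for a change. Followed as written, the plan gives a valid active-versus-sham comparison with no expected bias, provided order is independent of phase, which counterbalancing is meant to secure. Whether a phase term helps depends on an effect size that the documents do not supply. With perfectly known phase and 15 cycling women, the effect of omitting it runs from a 1.9% narrower interval to a 20% wider one, and at 0.5 SD with the minimum gap it is 0.3% wider. Misclassified phase shrinks the gain further.

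In a pilot-funded study (Section F) of up to 30 subjects in Aim 1, keeping the unadjusted paired difference as the estimate is a reasonable choice. The recorded dates still let the investigators confirm phase and describe how often it differed between sessions, and an analyst who wants a phase-adjusted sensitivity result can produce one without altering the plan. These sizes rest on the assumed 28-day two-phase cycle, random start day, 10 or 15 cycling women and the stated range of phase effects.
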